### 3.5.8.2. Audits and Inspections

The Investigator will permit direct access to Trial data and documents for the purpose of monitoring, audits and/or inspections by authorized entities such as but not limited to: the Sponsor or its designees and competent regulatory or health authorities. As such (e)CRFs, source records and other Trial related documentation (e.g. Investigator Site File, the Trial Master File, pharmacy records, etc.) must be kept current, complete and accurate at all times.

### 3.5.8.3. Datamanagement related to the use of the investigational device

#### Registration, authentication and verification

HCPs have to register to use ALICE-Pro before using the dashboard for the first time. They cannot log onto the dashboard without registration. Before clients can use the ALICE app, they first have to download it onto their smart device. The first time a client logs on to ALICE-Client, they will be asked to register and give permission to process personal data. No data can be accessed without being logged on to the app. After registration is completed, clients have to connect to a HCP dashboard and allow their data to be used and shared before an HCP can see their test and training data.

#### Permission

The client has to indicate that he/she allows the app to process their personal data when first registering on the app (including a privacy statement). This step is necessary for the HCP to identify who is using the app and for them to match training outcome to the right client.

#### Why

The data will be collected and processed based on 4 legal grounds:

1. Technical support from KUL to HCP and client
2. Medical service/treatment from HCP to client
3. Research purposes (efficacy, safety and usability of the app)
4. Future commercial activities (launch of the app through KUL spin off)

### **Data collection**

All data collected throughout the study will be pseudonymised and coded for KU Leuven researchers. HCPs will have the key which connects the code to each client. This key is stored on a secure location on the KU Leuven server.

When registering on the app, clients receive an anonymous code. This can only be linked to the ALICE-Pro dashboard after clients agree to the terms and conditions of the app and after they agree that data can be shared with their HCP. The client app will collect data that origin from the monitoring tasks, listening training exercises, pop-up questions and data that origin from the use of the app (analytics). No personal data are saved on the smart device. Training data are only saved on the clients' smart device when they are using the device without an internet connection. The data are transferred to the KU Leuven server once internet connection is established. The data collected through the ALICE-Client app can only be accessed through the ALICE-Pro dashboard after HCPs log on to the website.

The KU Leuven confirms that collection and processing during clinical trials is done in full compliance with the European Regulation 2016/679 of 27 April 2016 on the protection of natural persons with regard to the processing of personal data and on the free movement of such data (GDPR).

Participant data will be processed in accordance with the European General Data Protection Regulation (AVG/GDPR) and the Belgian Law (30 July 2018) on the protection of natural persons with regard to the processing of personal data. Research data resulting from the current project will be discarded after 25 years, according to KU Leuven/UZ Leuven research data policy regulations.

As the commissioner of the study, KU Leuven is the data controller of the personal data, which will be processed in the context of this study. Participants will be informed through the ICF about the purpose of the study, the data collected, the period for which data will be stored and the participants' rights. These rights may be exercised at any time during the study. All PIs have acquired certificates of good clinical practice. Applicants and researchers involved in the project will ensure that all research is carried out in accordance to the rules and regulations of scientific integrity of the KU Leuven.

### **Storage**

The file with the key to match each anonymised code to a specific client is stored on a secure location on the KU Leuven server. This key is used to automatically match the client with the training data in the pro portal.

All data input (from ALICE-Pro and ALICE-Client) will be safely stored on the KUL server. During the length of the study this data will not be encrypted based on the legal grounds that apply, to guarantee the technical and medical service will be delivered to the users of ALICE.

### **Procedures for data retention**

The file with the key to match each anonymised code to a specific client is stored on a secure location on the KU Leuven server. This key is used to automatically match the client with the training data in the pro portal.

All data input (from ALICE-Pro and ALICE-Client) will be safely stored on the KUL server. During the length of the study this data will not be encrypted based on the legal grounds that apply, to guarantee the technical and medical service will be delivered to the users of ALICE.

## Specified retention period

Research data resulting from the current project will be discarded after 25 years, according to KU Leuven/UZ Leuven research data policy regulations.

### 3.5.9. Amendments to the CIP

Unless for urgent reasons as specified in ICH-GCP E6(R2) section 4.5.4, amendments must not be implemented prior to EC and/or CA review and/or approval, as applicable.

In accordance with the Belgian law of May 7th 2004 regarding experiments on humans, the Sponsor may develop a non-substantial amendment at any time during the Trial. If a substantial amendment to the clinical Trial agreement or the documents that supported the original application for the clinical Trial authorisation is needed, the Sponsor must submit a valid substantial amendment to the Competent Authority (CA) for consideration, and to the EC for review and approval. The CA and/or EC will provide a response in accordance with timelines defined by applicable regulations. It is the Sponsor's responsibility to assess whether an amendment is substantial or non-substantial for the purpose of submission to the CA and/or EC.

Amendments to the Trial are regarded as 'substantial' when they are likely to have a significant impact on the safety or physical or mental integrity of the clinical Trial participants, or the scientific value of the Trial.

### 3.5.10. Deviations from the CIP

#### 3.5.10.1. Protocol / GCP compliance

The Trial must be performed in accordance with the protocol, current ICH and ICH-GCP guidelines, and applicable regulatory and country-specific requirements. ICH guidelines are an international ethical and scientific quality standard for designing, conducting, recording, and reporting studies that involve the participation of human participants. Compliance with this standard provides public assurance that the rights, safety, and well-being of Trial participants are protected, consistent with the principles that originated in the most recent version of the Declaration of Helsinki, and that the Trial data are credible, reliable and reproducible.

The Investigator and Trial team acknowledge and agree that prospective, planned deviations or waivers to the protocol are not permitted under applicable regulations on clinical studies. However, should there be an accidental protocol deviation, such deviation shall be adequately documented in the source documents and on the relevant forms and reported to the CI and Sponsor. Deviations should also be reported to the EC as part of the EC's continued review of the Trial (e.g. through the ASR, APR, etc.). Protocol deviations which are found to frequently recur, will require (immediate) action. The Investigator acknowledges that such recurring protocol deviations could potentially be classified as a serious violation of ICH and/or the protocol.

It is understood that "a serious violation" is likely to affect to a significant degree:

- the safety or physical or mental integrity of the Trial participants; or
- the scientific validity of the Trial

The Investigator is expected to take any immediate action required to protect the safety of any participant included in the Trial, even if this action represents a deviation from the protocol. In such cases, the Sponsor should be notified of this action and the EC at the Trial site should be informed according to local procedures and regulations.

### 3.5.11. Device accountability

In accordance with Annex VI, Part C of the Medical Device Regulation (EU) 2017/745 (MDR), only software which is commercially available on its own as well as software which constitutes a device in itself shall be subject to Unique Device Identifier (UDI) requirements.

For the clinical investigation, traceability shall be achieved by restricted access to the app, only subjects who are enrolled in the study and have signed the informed consent will be granted access (see section 3.5.6. for further details on the enrolment procedure)

### 3.5.12. Statements of compliance

The Trial will be conducted in compliance with the principles outlined in the requirements for **the European Regulation (EU) 2017/745 on Medical Devices (MDR)**, the ISO14155 as well as in compliance with ICH-GCP E6(R2) guidelines, other GCP guidelines, the most recent version of the Declaration of Helsinki, the Belgian law of May 7th 2004 regarding experiments on the human person (as amended) or the Belgian law of May 7th 2017 on clinical Trials with medicinal products for human use, as applicable, and with the EU General Data Protection Regulation 2016/679 (GDPR), the relevant Belgian laws implementing the GDPR, the Belgian Law of August 22nd 2002 on patient rights and all other applicable legal and regulatory requirements.

This clinical trial will not begin until it is approved by the ethical commission.

#### 3.5.12.1. Data protection and participant confidentiality

The Trial will be conducted in compliance with the requirements of the EU General Data Protection Regulation 2016/679 (GDPR), the relevant Belgian laws implementing the GDPR including the Belgian Privacy Act of 30 July 2018 on the protection of privacy in relation to the processing of personal data. Any collection, processing and disclosure of personal data, such as participant health and medical information is subject to compliance with the aforementioned personal data protection laws (cfr. Data Processing Annex (DPA) in Appendix). In case personal data is transferred outside the European Economic Area, safeguards will be taken to ensure that appropriate protection travels with the data in accordance with the GDPR. ([https://ec.europa.eu/info/law/law-topic/data-protection/international-dimension-data-protection/rules-international-data-transfers\\_en#documents](https://ec.europa.eu/info/law/law-topic/data-protection/international-dimension-data-protection/rules-international-data-transfers_en#documents))

Any personal data shall be treated as confidential at all times including during collection, handling and use or processing, and the personal data (including in any electronic format) shall be stored securely at all times and with all technical and organizational security measures that would be necessary for compliance with EU and national data protection legislation (whichever is more stringent). The Sponsor shall take appropriate measures to ensure the security of all personal data and guard against unauthorized access thereto or disclosure thereof or loss or destruction while in its custody.

#### Financing

This study is sponsored by the KU Leuven internal funds C3/21046 (PI: [name] [name])

**Financial arrangement: Investigational sites will not receive a reimbursement for participation in this study.**

#### No fault insurance

The Participating Site, the Investigator and Sponsor shall have and maintain in full force and effect during the term of this Trial, and for a reasonable period following termination of the Trial, adequate insurance coverage for: (i) medical professional and/or medical malpractice liability, and (ii) general liability.

#### For Belgian Participating Sites

Art 29 of the Belgian Law relating to experiments on human persons dated May 7th, 2004 applies. Prior to the start of the Trial, the Sponsor shall enter into an insurance contract in order to adequately cover Trial participants from Belgian sites in accordance with art. 29 of the said law.

### 3.5.13. Informed consent process

The Trial will be conducted only on the basis of prior informed consent by the Trial participants and/or their legally authorized representative(s). As such, no Trial-related procedures will be conducted prior to obtaining written informed consent from potential Trial participants.

The process for obtaining and documenting initial and continued informed consent from potential Trial participants will be conducted in accordance with ICH-GCP E6(R2), applicable regulatory requirements and internal Standard Operating Procedures (SOPs).

All originally signed obtained Informed Consent Forms (ICFs) must be retained/archived in the Investigator Site File (ISF) at the Participating Site and must not be destroyed (even when a scanned copy is available) before expiration of the legal archiving term as defined in the protocol section entitled “Archiving”.

Participants may voluntarily withdraw consent to participate in the Trial for any reason at any time. The participant's request to withdraw from the Trial must always be respected without prejudice or consequence to further treatment. Consent withdrawal will be documented in the participant's medical record.

Trial data and samples collected before withdrawal can be used in the trial. No new trial data or samples will be collected after withdrawal of the participant.

#### 3.5.13.1. Description of the general process for obtaining informed consent, including the process for providing subjects with new information, as needed.

Before clients enter the study, they will be informed about the purpose of the study, its goals, what is expected from the participant, the data collected, the period for which data will be stored and the participants' rights by their HCP/the researcher and also through the informed consent form (ICF). All clients receive an informed consent form and an informed consent signature is obtained for all clients who agree to participate in the study.

Clients will be informed that they can withdraw from the study without any reason (and without consequence for their follow-up in the hearing centre or at UZ Leuven, if applicable). These rights may be exercised at any time during the study. Clients cannot participate in the study without signing the informed consent form.

Besides an informed consent form, clients have to agree to the terms and conditions and the privacy statement of the ALICE app. These include information on how data are processed and stored. Clients have to indicate that they allow their data to be collected and shared within the study.

#### 3.5.13.2. Description of the informed consent process in circumstances where the subject is unable to give it

No participants will be included in the study who are unable to give informed consent themselves.

### 3.5.14. Adverse events, adverse device effects and device deficiencies

#### 3.5.14.1. Definitions

The definitions and reporting requirements adopted in this Clinical Investigation Plan (CIP) are based on the Medical Device Regulation (EU) 2017/745 and the MDCG 2020-10/1 European guideline.

##### **Adverse Event (AE)**

An AE is any untoward medical occurrence, unintended disease or injury or any untoward clinical signs (including an abnormal laboratory finding) in subjects, users or other persons, in the context of a clinical investigation, whether or not related to the investigational medical device.

Note:

- a. This definition includes events related that are anticipated as well as unanticipated events
- b. This definition includes events occurring in the context of a clinical investigation related to the investigational device, the comparator or the procedures involved.

##### **Serious Adverse Event (SAE)**

A SAE is any adverse event that led to any of the following:

- a) death
- b) serious deterioration in health of the subject, that resulted in any of the following:
  - life-threatening illness or injury
  - permanent impairment of a body structure or a body function
  - hospitalisation or prolongation of patient hospitalisation
  - medical or surgical intervention to prevent life threatening illness or injury or permanent impairment to a body structure or a body function
  - chronic disease
- c) foetal distress, foetal death or a congenital physical or mental impairment or birth defect

##### **Adverse Device Effect (ADE)**

An ADE is an adverse event related to the use of an investigational medical device.

##### **Serious Adverse Device Effect (SADE)**

A SADE is an adverse device effect that has resulted in any of the consequences characteristic of a serious adverse event.

An Unanticipated Serious Adverse Device Effect is an effect which by its nature, incidence, severity or outcome has not been identified in the current risk assessment.

##### **Device Deficiency (DD)**

A DD is any in the identity, quality, durability, reliability, safety or performance of an investigational device, including malfunction, use errors or inadequacy in information supplied by the manufacturer.

Possible adverse events related to device deficiency

- Software malfunctions (bugs)
- Software compatibility/interoperability

##### **Mitigation of adverse events related to malfunctions of the software**

Software malfunction: software has been developed following the IEC 62304 standard, taking into account all possible risks in the design and development phase (risk-based approach, ISO 14791, see

IB). However the occurrence of small software malfunctions remains high, resulting in a significant risk of low harm for the users of the app.

If bugs or deficiencies occur clients can contact their hearing care professional at the hospital or hearing centre, or report the issue directly to the app developers by email. The developers are not directly involved in the clinical study. Moreover, continuity of the standard of care is always guaranteed by their HCP.

**Software compatibility/interoperability:** Software can only be used with other CE-marked devices (tablet or smartphone) to ensure a safe output level (which is regulated by EU standard EN 50332 in Europe since 2013). This is clearly stated in the IFU.

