### 3.5.4.2. Residual risks associated with the investigational device, as identified in the risk analysis report

(See Risk analysis in IB). In summary, only 1 risk remains significant after implementation of the control measures. The occurrence of (small) software failures remains high, but the severity of the harm is in our case considered to be minimal as the device is used as an additional service on top of the standard of care. As the risks are associated with negligible potential harms, we consider the harm and the risk as acceptable, and we can, with certainty, say that the benefits of the app (as already demonstrated in section 3 of the IB) outweigh these minimal risks.

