#### 3.5.14.4. Recording and reporting of Device Deficiencies

**Each Device Deficiency must be documented by the Investigator in the source documents and reported to the Sponsor on a Device Deficiency form.**

If the Device Deficiency lead to the occurrence of a (S)ADE, the (S)ADE must also be reported by the Investigator to the Sponsor on the appropriate forms and within the specified timelines.

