### Sponsor's reporting of Serious Adverse Events and Device Deficiencies

The Sponsor is responsible to report to the CA's where the clinical investigation has commenced:

- Any SAE that has a **causal** relationship with the investigational device, the comparator or the investigation procedure or where such causal relationship is reasonably possible;
- Any Device Deficiency that might have led to a SAE if:
  - a) Appropriate action had not been taken or,
  - b) Intervention had not occurred or,
  - c) If circumstances had been less fortunate
- New findings/update in relation to already reportable events.

These 'reportable events' must be reported within the following timelines:

- A reportable event which results in imminent risk of death, serious injury, or serious illness that requires prompt remedial action for other patients/subjects, users or other persons or a new finding to it must be reported immediately, but not later than **2 calendar days** after awareness by

the sponsor of a new reportable event or of new information in relation with an already reported event.

- Any other reportable event or a new finding/update to it must be reported immediately, but not later than **7 calendar days** following the date of awareness by the sponsor of the new reportable event or of new information in relation with an already reported event.

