### Overview reporting requirements

	WHAT	HOW	TO	TIMELINES
Investigator	AE	AE form	sponsor	as defined in protocol
	SAE	SAE form	sponsor	asap, but no later than 3 calendar days after awareness
	Device Deficiency (DD)	DD form + AE/SAE form (if applicable)	sponsor	as defined in protocol (exception: within 3 calendar days if considered reportable event)
	death	SAE form	sponsor	asap
Sponsor	all reportable events (of all participating sites)	EU SAE report form (excel) 	
 
CA for Belgium -> FAGG: via mail to [contact]
 
PI's of participating sites
 
	asap, but no later than 
 
2 calendar days (in case of risk of death or serious injury/illness that requires prompt remedial action for other patients, users or other persons)
 
7 calendar days (all other reportable events)
 

	death	SAE form + narrative	
 
CA for Belgium -> FAGG: via phone and mail
 
	asap

 The SAE report form in excel format can be downloaded from the following web page: [https://ec.europa.eu/health/sites/health/files/md\\_sector/docs/md\\_mdcg\\_2020-10-2\\_guidance\\_safety\\_report\\_form\\_en.xlsx?web=1](https://ec.europa.eu/health/sites/health/files/md_sector/docs/md_mdcg_2020-10-2_guidance_safety_report_form_en.xlsx?web=1)

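### Clients may email malfunctions straight to the app developers, and nothing in the plan brings those reports back to the investigator, so device deficiencies can go unlogged and expedited timelines can be missed

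*Combined protocol and SAP*

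**What the plan says.** Under Device Deficiency (DD) in 3.5.14.1, a deficiency is defined as "including malfunction, use errors or inadequacy in information supplied by the manufacturer", so an ordinary software bug is a device deficiency. Section 3.5.14.4 makes no exceptions: "Each Device Deficiency must be documented by the Investigator in the source documents and reported to the Sponsor on a Device Deficiency form".

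The section headed Mitigation of adverse events related to malfunctions of the software gives clients a choice. They may contact their hearing care professional, or "report the issue directly to the app developers by email. The developers are not directly involved in the clinical study".

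The monitoring plans in 3.5.6.2, 3.5.6.3 and 3.5.6.4 describe a different chain. The client goes first to the local PI (in Arm 3, the local study team). For app problems the site contacts the Coordinating Investigator, and the in-house developers come in only if technical help is needed.

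On importance, 3.5.4.2 states that "only 1 risk remains significant after implementation of the control measures" and then identifies it: "The occurrence of (small) software failures remains high", with minimal severity. The malfunction section agrees: "However the occurrence of small software malfunctions remains high, resulting in a significant risk of low harm for the users of the app".

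On timing:
- Timelines for reporting (3.5.14.3) gives 24 hours from awareness by trial staff for serious adverse events and adverse events of special interest.
- The Overview reporting requirements table gives, for deficiencies, "as defined in protocol (exception: within 3 calendar days if considered reportable event".
- Section 3.5.14.5 gives the sponsor 2 or 7 calendar days from its own awareness. Reportable events there include "Any Device Deficiency that might have led to a SAE if" one of three listed conditions is met.

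**The concern.** An investigator cannot document a deficiency that was reported only to someone else. A client who follows the email instruction to the letter has done what the plan asks, yet the investigator may never learn of the fault.

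Two things are at stake. The first is the completeness of the deficiency record in a pre-market study, for the one risk still rated significant after control measures. That record is the natural check on the assessment that failures are frequent but harmless. The second is timeliness. An email may describe stimuli that are too loud, or a data-security problem. Both are listed as events of special interest and are due on the serious-event timeline. An email may also describe a fault that could have led to a serious event. In each case the message reaches people whom the plan does not name as part of the safety reporting chain.

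**Working it through.** The plan gives no figure to reproduce, so the check sets the sections side by side.

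1. **Is an emailed bug a device deficiency?** Yes. The definition in 3.5.14.1 includes malfunction.

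2. **Does every deficiency need an investigator's form?** Yes. Section 3.5.14.4 covers each one, however it was reported.

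3. **Does the email route pass through the investigator?** No. It runs from client to developer, while the monitoring plans run from client to site to Coordinating Investigator to developer. The two chains go in opposite directions, and no step is written from developer back to site.

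4. **Does another section close the gap?**
 - Onboarding (3.5.6.2 to 3.5.6.4) covers a procedure for malfunctions but does not give its content. The only content written in this document is the malfunction section, which offers the email route.
 - Section 3.5.14.3 has investigators ask about adverse events at each contact. It does not mention deficiencies.
 - Section 3.5.14.5 has the sponsor evaluate deficiencies promptly, but nothing sends emailed ones to the evaluator.

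5. **Would questioning at the final visit be in time?** Arms 1 and 3 have visits at 0 and 8 weeks, and 8 × 7 = 56 days. A fault emailed on day d and first mentioned at the final visit reaches the investigator 56 − d days later. That lag is 3 days or less only if d ≥ 53, and 7 days or less only if d ≥ 49. A fault emailed on day 14 would surface 42 days later. Questioning at that visit can add to the count, but for most of the use period it is too late for expedited reporting. Arm 2 has three visits and 4 to 6 weeks of app use; the visit days are in a figure that is not shown.

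6. **Which clock does an email start?** The 24-hour clock starts when trial staff become aware, and the 2- or 7-day clock when the sponsor does. The developers are described as not directly involved in the study. They are also called in-house, and 3.5.2.4 places development in the KU Leuven research group. Section 3.5.8.3 calls KU Leuven the commissioner of the study. There are two readings. If developers count as neither trial staff nor sponsor, no clock starts until someone else hears. If their receipt counts as sponsor awareness, the clock can run out with nobody in the safety chain informed. The plan does not say which applies.

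7. **Can the size be computed?** No. Section 3.5.7.1 gives the planned app users: 75 + 60 + 60 = 195 with hearing aids, plus 15 with cochlear implants, about 210. The number of unlogged deficiencies would be 210 × malfunctions per user × share reported by email only × share never passed to the site. The document gives none of the last three factors, so the unlogged share could lie anywhere from none to all.

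**The case against.** The strongest reply is that silence about forwarding does not show that forwarding is absent. Section 3.5.14.4 binds for every deficiency, a malfunction procedure is taught at onboarding, and the instructions for use, the investigator's brochure and the data management plan are not part of this document. Questioning about adverse events at each contact should also bring out some of these problems, because events of special interest are adverse events and software bugs are listed among possible adverse events related to deficiencies. Harm is described as minimal, so few malfunctions should meet the near-serious test in 3.5.14.5.

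Much of this stands. It limits the point to what can happen and keeps its size unknown. It does not remove the conflict: the plan itself offers a route that leaves the investigator unaware, and late questioning does not meet an expedited timeline.

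A reader might infer more than the documents support:
- **That deficiencies are undercounted, or that the record is incomplete by design.** The text shows that reports can be lost, not that they are. A hand-over may exist elsewhere.
- **That the deficiency count is a main safety result.** The endpoint lists in 3.5.6.2 to 3.5.6.4 contain no such count.
- **That a client's email breaches pseudonymisation.** Section 3.5.8.3 pseudonymises study data for KU Leuven researchers but also lists technical support from KU Leuven to clients as a ground for processing, so identified contact is foreseen.
- **That the email route should be closed.** That would remove a reporting channel and might reduce reporting. The defect is the missing return path.

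**Conclusion.** The point holds as a conflict between sections with a practical consequence. The malfunction section permits a reporting route that does not fit 3.5.14.4 or the support chain in the three monitoring plans, and no section sends emailed reports back to the study. Device deficiencies can therefore go unlogged, and an emailed event of special interest or a deficiency that might have led to a serious event can miss the timelines in 3.5.14.3 and 3.5.14.5.

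The effect falls on the app group's safety and performance record, about 210 planned users. Its size is unknown, few events should need expedited reporting, and the efficacy comparison is not affected. The conclusion assumes that no hand-over is written in the documents not available here. If one is, what remains is to state it in this plan. The point should be fixed because it touches the only risk still rated significant and costs little to close.

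**What to change.** Reconcile the malfunction section with 3.5.14.4 and with the monitoring plans in 3.5.6.2, 3.5.6.3 and 3.5.6.4, as follows:

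1. Keep the email route, but require developers to forward each trial participant's message to the Coordinating Investigator on the day it arrives.
2. Have the Coordinating Investigator pass it to the local PI, who applies the participant code and completes the deficiency form, plus the form for an adverse event or event of special interest where applicable. Coding belongs at the site because 3.5.8.3 gives the code key to the hearing care professionals and describes no access for developers.
3. Reconcile the developer mailbox with the deficiency log at monitoring visits and before database lock.
4. State when sponsor awareness starts for a report received by email.

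While editing these sections, also reconcile the investigator's deadline for serious adverse events, which is 24 hours in Timelines for reporting but up to 3 calendar days in the overview table.

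The cost is a wording change, a small forwarding workload for the developers and the Coordinating Investigator, and possibly a higher recorded deficiency count.
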